## 5.2 Screen Failures

Screen failures are defined as subjects who consent to participate in the clinical study but are not subsequently enrolled. A minimal set of screen failure information is required to ensure transparent reporting of screen failure subjects. Minimal information should include demography, screen failure details, eligibility criteria, and any serious adverse event (SAE).

## 6.0 Study Intervention

Bone marrow aspiration will be completed on all subjects randomized to Arm 1. Small volume lipoplasty will be completed on all subjects randomized to Arm 2.

Prior to the knee injection, all samples will undergo point of care testing. If the BMAC, SVF final products or the UCT MSCs do not meet the final product acceptance criteria, as outlined in the Operations Manual, the subject will be discontinued from the study. The study team will maintain contact with the subject during the subsequent 30 days including in-person visit to assess any potential AEs and SAEs that the subject may have experienced after the study

treatment procedure. Subject will be withdrawn after 30 days if all study-related AEs are resolved.

All injections will be done into the knee joint via ultrasound guidance using a standard approach as described in the Operations Manual. Prior to the study injection, the treating investigator may aspirate excess synovial fluid for future cell characterization testing at MC3M (see Section 8.2.14).

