## **7.0 Subject Discontinuation/Withdrawal**

### **7.1 Subject Discontinuation**

A subject must be discontinued from the trial for any of the following reasons:

- Unacceptable adverse experience
- Investigator's decision to withdraw the subject for safety, behavioral, compliance, or administrative reasons
- If the BMAC, SVF final products or UCT MSCs do not meet final product acceptance criteria outlined in the Operations Manual

For those subjects who discontinue participation early, each subject will be followed for serious adverse events (90 days) that are ongoing at the time of subject discontinuation. Monitoring of the serious adverse event may be done by telephone per treating investigator discretion. All AEs potentially related to study participation will be followed until resolution prior to study completion or early termination of subject. Open AEs that are unrelated to the study participation will not be followed beyond study completion or subject's early termination.

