#### **8.1 Study Visit Assessments**

##### **8.1.1 Screening Visit (Visit 1)**

- Administer informed consent and HIPAA Authorization
- Collect demography
- Collect medical and surgical history
- Collect prior and concomitant medications
- Collect Knee Osteoarthritis History
- Review inclusion and exclusion criteria
- Focused knee assessment
- Perform vital signs
- Knee MRI (only if the subject is eligible for the study)
- Collect subject PROs
- Perform pregnancy test (on female subjects of childbearing potential)
- Blood Collection (safety labs)
- Once all screening assessments are complete and eligibility has been confirmed by the treating investigator, the subject may be randomized.
- Schedule the subject for the appropriate Treatment Visit procedure based on randomization

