### 8.1.2 Treatment Visit (Visit 2, Day 0)

- Collect concomitant medications
- Focused knee assessment (if required, at the discretion of the treating investigator)
- Perform vital signs
- Assess adverse events
- Perform pregnancy test (on female subjects of childbearing potential)
- Confirm subject eligibility
- Study procedures (**depending on subject randomization**)
  1. Arm 1-BMAC Treatment: bone marrow aspiration, cell processing and product release criteria testing
  2. Arm 1-CSI Treatment: bone marrow aspiration, cell processing, product release criteria testing and CSI preparation
  3. Arm 2-SVF Treatment: lipoaspirate procedure, cell processing, and product release criteria testing
  4. Arm 2-CSI Treatment: lipoaspirate procedure, cell processing, product release criteria testing and CSI preparation
  5. Arm 3-UCT Treatment: dispense UCT-MSCs, dose preparation, and product release criteria testing
  6. Arm 3-CSI Treatment: CSI preparation
- Perform arthrocentesis and knee injection
- Process and store samples for cell characterization (details are described in the Laboratory Manual)
- Home physical therapy program to begin post procedure day 8, see Appendix 12.1. Instructions for at home physical therapy will be provided to the subject by the study staff.

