### **9.3 Efficacy Analyses**

The statistical analysis plan (SAP) has been developed and describes the subject populations to be included in the analyses, and procedures for accounting for missing, unused, and spurious data. This section is a summary of the planned statistical analyses of the primary and secondary endpoints.

The primary analysis of the data will be performed according to subjects' original treatment assignment (i.e., intention-to-treat analyses) regardless of their compliance to treatment and the inclusion of all data from all subjects randomized in the final analysis.

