#### **9.3.2 Primary and Secondary Efficacy Analyses**

Eight separate repeated-measures analysis will be performed on the eight efficacy variables described above. Each of the eight variables will be used as a dependent variable. The following model building method will be used for each analysis. Using Statistical Analysis System (SAS) MIXED Procedure (version 9.4; SAS Institute, Cary, NC), a linear mixed model will be fit on each efficacy variable. The model will include site, treatment arm, time on study (baseline and 1, 3, 6, 9

and 12 months on study), and treatment arm by time interaction as fixed effects. Subject ID will be the random effect. A compound-symmetric variance-covariance form in repeated measurements will be assumed and robust estimates of the standard errors of parameters will be used to perform statistical tests and construct 95% confidence intervals. The model-based means are unbiased with unbalanced and missing data, assuming missing data are non-informative. A P-value  $\leq 0.05$  will be considered statistically significant for all the terms in the mixed model. The statistical test for interaction between time on study and treatment will be the overall hypothesis test to determine whether efficacy variables in the four treatment arms changed significantly during 12 months of follow-up. If mean scores in the treatment arms are consistently different or similar over time (i.e., no statistical interaction) then the main effect test for treatment will be used as the primary hypothesis test to compare the treatment arms. The primary study results from this model will be the mean score and 95% confidence interval for each of the 4 treatment arms and the treatment mean differences and 95% confidence intervals.

Assuming a significant treatment effect on efficacy score change is identified (i.e., the interaction test is significant at  $P = 0.05$ ) then the six pairwise treatment comparisons on pain score change will be performed. A Bonferroni correction ( $p=0.05/6=0.0083$ ) for multiple comparisons will be applied. Specific statistical tests on efficacy score change will be done within the framework of the mixed effects linear model. All statistical tests will be 2-sided and adjusted for multiple comparisons. The same Bonferroni method will be used if the statistical interaction between treatment group and time on study is not significant but the main effect test for treatment is significant.

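### Randomised subjects whose cell product fails acceptance are withdrawn with no later pain scores required, which undercuts the intention-to-treat claim and could overstate the cell-versus-steroid effect

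*Combined protocol and SAP*

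**What the plan says.** Section 8.1.1 places randomisation at the end of screening: "Once all screening assessments are complete and eligibility has been confirmed by the treating investigator, the subject may be randomized". Harvest, processing and release testing follow on Day 0 (section 8.1.2).

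Section 6.0 states that if the BMAC or SVF final products or the UCT cells "do not meet the final product acceptance criteria, as outlined in the Operations Manual, the subject will be discontinued from the study". Section 7.1 lists the same event among the reasons for mandatory discontinuation, when the products "do not meet final product acceptance criteria outlined in the Operations Manual".

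The follow-up stated for these subjects concerns safety only. Section 6.0 asks for contact over 30 days, including an in-person visit for adverse events, and then: "Subject will be withdrawn after 30 days if all study-related AEs are resolved". Section 7.1 adds 90 days of follow-up for serious events still ongoing. No section asks for VAS or KOOS after this kind of discontinuation.

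Section 9.3 says that the primary analysis follows original assignment, "regardless of their compliance to treatment and the inclusion of all data from all subjects randomized in the final analysis". Section 9.3.2 excludes missing values from the mixed model and rests on this statement: "The model-based means are unbiased with unbalanced and missing data, assuming missing data are non-informative".

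Section 7.4 treats a similar situation differently. Subjects declared treatment failures keep giving pain scores to one year, and reduction of bias is the stated reason.

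Section 8.1.2 also shows that release testing is not confined to subjects who will receive cells. For steroid subjects in Arm 1 it lists "Arm 1-CSI Treatment: bone marrow aspiration, cell processing, product release criteria testing and CSI preparation", and the Arm 2 entry is parallel. For Arm 3 it lists only "Arm 3-CSI Treatment: CSI preparation".

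**The concern.** Product failure happens after randomisation and determines whether the subject is injected. Removing these subjects and collecting no further outcomes means the estimate describes subjects whose product passed, while the report will call it intention-to-treat. The first post-baseline PROs are due at Day 30, about when the safety follow-up ends, so these subjects may contribute a baseline score and nothing else.

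The loss need not be even across groups. BMAC and SVF come from the subject's own tissue, whereas UCT is a manufactured third-party product. Section 2.2 says that donor age, tissue site and isolation process may affect the adipose cell analysis. The subjects lost may therefore differ between the products the trial sets out to rank. The pooled steroid group is affected differently again, because one third of it (Arm 3) has no product that can fail.

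**Working it through.** **Reproducing the plan's figure.** Section 9.2 assumes a mean VAS decline of 2.5 points with cells and 1.0 with steroid, SD of change 3.5, 121 per group and a two-sided 5% t-test, and states 91% power. The noncentral t gives 91.3%, so the inputs are used as the plan uses them.

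**What the planned model does with a baseline-only subject.** Under compound symmetry with correlation ρ, the model's Month 12 mean for a group with such subjects is

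(mean at Month 12 in injected subjects) + ρ × (baseline mean of all − baseline mean of injected).

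If failure is unrelated to baseline pain, the second term averages zero. The estimated decline is then that of injected subjects, 2.5 points, whatever happened to the others. A simulation (120 per group, ρ = 0.5 assumed, SD of change 3.5, 20,000 runs, Monte Carlo error 0.003) agrees: the model estimate stays at 1.50 for every failure rate tried. Following everyone gives about 1.35 at 10% failure if uninjected subjects improve by 1 point, and 1.25 if they do not change. The simulation illustrates the algebra and is not separate evidence about this trial.

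**Size of the overstatement.** Let f be the share of products that fail and m the mean decline in uninjected subjects. Take 2.5 as the mean in injected subjects.

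- A: only cell-group subjects are removed, m = 1.0. As-randomised effect = 2.5(1 − f) + 1.0f − 1.0 = 1.5 − 1.5f. Overstatement 1.5f.
- B: only cell-group subjects are removed, m = 0. Effect = 2.5(1 − f) − 1.0 = 1.5 − 2.5f. Overstatement 2.5f.
- C: m = 0 and the 80 of 120 steroid subjects in Arms 1 and 2 are removed at the same rate. Effect = 2.5(1 − f) − (1 − 80f/120) = 1.5 − 1.83f. Overstatement 1.83f.

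The documents give no value for f; the range below is an assumption. Percentages are relative to the as-randomised effect.

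| f | A | B | C |
|---|---|---|---|
| 1% | 0.015 (1.0%) | 0.025 (1.7%) | 0.018 (1.2%) |
| 2% | 0.03 (2.0%) | 0.05 (3.4%) | 0.04 (2.5%) |
| 5% | 0.075 (5.3%) | 0.125 (9.1%) | 0.09 (6.5%) |
| 10% | 0.15 (11.1%) | 0.25 (20.0%) | 0.18 (13.9%) |
| 15% | 0.225 (17.6%) | 0.375 (33.3%) | 0.275 (22.4%) |

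**Bias or power?** Losing the subjects costs little power in itself. At the plan's two-sided 5% level, with 120 steroid subjects and 120(1 − f) in the cell group, power for 1.5 points is still 90% at f = 5% and at f = 10%. If all 120 are followed and the effect is the diluted one, power is 86–88% at 5% and 79–85% at 10%. The problem is therefore mainly what the estimate means, and only secondarily its precision.

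**The case against.** The strongest reply is that neither size nor direction can be established from the documents. No failure rate is given. The upper end of the range also sits badly with the 90% retention in section 9.2, which allows 48 losses in 480. If that figure counts every randomised subject, 10% failure among the 360 cell-group subjects (36) uses three quarters of the allowance, and 15% (54) exceeds it. At 1–2% the overstatement is 0.015 to 0.05 points, against a standard error of about 0.45 for the contrast (3.5 × √(2/120)). If uninjected subjects improved as much as injected ones, for example after other treatment, there would be no bias, and if they improved more it would reverse. The 2.5 points in section 9.2 might also already be an as-randomised mean. All of this stands, and it limits the claim to a possible bias of unknown size.

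A second reply is that there is no literal contradiction: section 9.3 governs the analysis of collected data, section 6.0 governs what is collected, and the baseline scores of these subjects do enter the model. As wording that is fair. But an analysis meant to hold regardless of compliance has little content for subjects whose outcomes stop being measured because they were not treated.

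A third is that unseen documents may help. The separate SAP cited in section 9.3 may hold a sensitivity analysis, and the Operations Manual may say how release criteria apply to steroid subjects. The manual could settle that clarification. Neither can recover pain scores that were never collected.

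**Conclusion.** The concern holds. Followed as written, sections 6.0 and 7.1 remove randomised subjects for a post-randomisation reason and require no further primary outcome from them, and the planned model does not repair this. It is also inconsistent with the principle the protocol adopts in section 7.4.

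The overstatement of the 1.5-point VAS effect is between 1.5f and 2.5f under the assumptions above: negligible at 1%, material at 10%. It rests on an assumed f, on uninjected subjects improving by 0 to 1 point, and on 2.5 points being the mean in injected subjects. Because the size is unknown and may be small, this is a change that should be made and not a fatal flaw. The loss cannot be made good after the event.

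**What to change.** In sections 6.0 and 7.1, separate not being injected from being withdrawn from follow-up. Unless consent is withdrawn, continue VAS, KOOS and concomitant-treatment collection at the scheduled PRO time points to Month 12, with section 7.4 as the precedent. Analyse these subjects in their assigned group, add an injected-only analysis as sensitivity, and report failure counts by arm and treatment. Sections 6.0 and 8.1.2 should also be reconciled so that it is clear what a failed, unused product means for steroid subjects in Arms 1 and 2. None of this changes who is injected.

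The cost is up to five PRO contacts (Months 1, 3, 6, 9 and 12) per uninjected subject. At 2–15% failure among 360 cell-group subjects that is about 7–54 subjects and 5 × f × 360 = 36–270 contacts. If the 80 Arm 1 and Arm 2 steroid subjects are also affected, it is about 9–66 subjects and 5 × f × 440 = 44–330 contacts. Month 1 could coincide with the in-person safety visit, and Month 9 is by telephone for everyone. Months 3, 6 and 12 are clinic visits, so telephone collection there would change the mode of the primary outcome for these subjects.

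The same principle would sensibly cover other discontinuations, such as those for adverse experience or by investigator decision in section 7.1. Those contacts are not costed here.

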## **6.1 Study Intervention(s) Administered:**

### **6.1.1 Autologous Bone Marrow Concentrate (BMAC)**

Bone Marrow Aspiration Concentrate (BMAC) is a standard Orthobiologic injection done for patients with knee osteoarthritis. This is a one step, same day procedure that involves harvesting of bone marrow aspirate (BMA) from the posterior superior iliac spine (PSIS) and then following centrifugation in an FDA approved device (EmCyte GenesisCS Pure BMAC®-60 ml), will be injected back into the knee joint for therapeutic effect. Details of the procedure are described in the Operations Manual.

### **6.1.2 Adipose-derived Stromal Vascular Fraction (SVF)**

Lipoaspirate is obtained from a mini-lipoaspirate procedure. The lipoaspirate will then be enzymatically digested to produce a stromal vascular fraction (SVF) that will be injected into the knee joint. Details of the procedure are described in the Operations Manual.

### **6.1.3 Mesenchymal Stem Cells derived from Umbilical Cord Tissue (UCT)**

Umbilical Cord Tissue has not been extensively studied for injections in knee Osteoarthritis. For this study, each study site will be provided with cryopreserved doses of cord tissue MSCs. These MSCs were cryopreserved at P2 culture in plasmalyte A + 5% human serum albumin in 5 finger cryobags containing 20 million cells in 4 mL and stored under liquid nitrogen until shipment to the study sites. Cells will be transported in a dry shipper and thawed at the point of care. The dose of MSCs will be thawed, aspirated from the cryobag into a sterile syringe and directly injected into the study subject's knee. Details of the procedure are described in the Operations Manual.

### **6.1.4 Corticosteroid Injection**

A standard and routine procedure in the care of subjects with Osteoarthritis is an injection of corticosteroids into the knee joint. Corticosteroids have been shown to be effective for short-term relief of knee pain associated with Osteoarthritis and will serve as our standard of care procedure to compare to our cellular treatments. Details of the procedure are described in the Operations Manual.

## **6.2 Measures to Minimize Bias: Randomization and Blinding**

The proposed clinical trial will allow for the unbiased evaluation of the efficacy of adult autologous versus third party stem cells and compare that efficacy to a gold standard treatment (e.g. corticosteroids).

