### 1.1 Synopsis

Title of Study	Randomized multicenter phase 3 single-blind trial comparing the efficacy of corticosteroid control to mesenchymal stem cell preparations from autologous bone marrow concentrate (BMAC), adipose derived stem cells in the form of Stromal Vascular Fraction (SVF), and third party human mesenchymal stem cells manufactured from umbilical cord tissue (UCT) for the treatment of unilateral Knee Osteoarthritis (OA).
Study Objectives	To identify a superior source of stem cells for the treatment of osteoarthritis and validate its advantages over corticosteroid injections as traditional gold standard treatment. The primary efficacy co-outcomes are: a change in the visual analog score (VAS) pain score and a change in the pain subsection of the knee injury and osteoarthritis outcome (KOOS) score. Secondary endpoints include total KOOS score, Magnetic Resonance Imaging (MRI) and additional patient reported outcomes (PROs).
Study Design	Multicenter prospective single-blinded randomized controlled clinical trial. The study will include a parallel design using a blocked central randomization scheme of 1:1:1:1. Subjects will be allocated to three different arms with a 3:1 assignment. Autologous bone marrow concentrate (n=120): corticosteroid (n=40), umbilical cord tissue (n=120): corticosteroid (n=40), and adipose derived SVF (n=120): corticosteroid (n=40).

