## 2.3 Benefit/Risk Assessment

### 2.3.1 Procedural-Related Risks

Subjects may experience pain and/or discomfort during and after the bone marrow and liposuction procedures despite the local anesthesia.

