### **6.2.2 Implementation of Randomization and Blinding**

Subjects randomized to Arm 1 or Arm 2 will undergo a procedure (bone marrow aspiration or liposuction) but will only receive one of the possible injections. For instance, subjects randomized to the control portion of Arm 1 will undergo a bone marrow aspiration but will receive a blinded corticosteroid injection. The bone marrow aspirate will still be processed and used to help quantify cell characteristics. Subjects randomized to Arm 3 will not undergo the procedures mentioned above. They will be blinded and receive either the stem cell injection or the corticosteroid injection.

Four hundred eighty subjects will be randomly assigned to treatment in this multicenter trial. Subjects at each clinical site will be randomized to ensure the trial is single-blind with a 1:1 allocation ratio across the four treatment groups.

One hundred twenty subjects will be randomized at each of 4 clinical sites. Arm 1: Forty subjects will be randomized with a 3:1 allocation ratio (bone marrow derived MSCs versus corticosteroid injection; 30:10). This same implementation plan will be used to randomize 40 subjects to Arm 2 (adipose derived MSCs versus corticosteroid injection) with a 3:1 allocation ratio and to randomize 40 subjects to Arm 3 (umbilical cord tissue MSCs versus corticosteroid injection) with a 3:1 allocation ratio.

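### The cell-versus-cell tests compare harvest procedure plus product, with the procedure known to the subject, so section 6.2 should not call autologous versus third-party efficacy an unbiased evaluation

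*Combined protocol and SAP*

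**What the plan says.** The synopsis (1.1) puts the comparison of cell sources first among the objectives: "To identify a superior source of stem cells for the treatment of osteoarthritis". Validation against corticosteroid follows. Section 6.2, under the heading on minimizing bias, states that the design permits an "unbiased evaluation of the efficacy of adult autologous versus third party stem cells".

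The procedures are fixed by arm. Section 6.0: "Bone marrow aspiration will be completed on all subjects randomized to Arm 1", and "Small volume lipoplasty will be completed on all subjects randomized to Arm 2". Section 6.2.2: "Subjects randomized to Arm 3 will not undergo the procedures mentioned above". No sham harvest is described for Arm 3. Within each arm, subjects are allocated 3:1 to cells or CSI without being told which; for Arm 3 the text reads "They will be blinded and receive either the stem cell injection or the corticosteroid injection".

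Section 9.2 names VAS pain and the KOOS pain subscale as the primary endpoints, both reported by the subject. Sections 9.3.2 and 9.3.3 use one four-level treatment factor (CSI as reference, BMAC, ADP, UCT), with CSI pooled over the three arms and no term for the procedure. After a significant overall test, "then the six pairwise treatment comparisons on pain score change will be performed", each at 0.0083. Three of those six pairs are cell versus cell.

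**The concern.** Having a harvest is not something a subject can be unaware of. Section 2.3.1 warns: "Subjects may experience pain and/or discomfort during and after the bone marrow and liposuction procedures despite the local anesthesia". A BMAC recipient and a UCT recipient therefore differ in two ways: the product in the knee, and the experience and knowledge of a marrow aspiration. The outcome is a pain score that the subject supplies. Section 4.2 itself notes, from an earlier trial, that saline-injected knees also did well, so response without active cells is a recognized possibility in this setting.

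Randomization does not remove this, because the difference arises after assignment. A larger sample or the Bonferroni correction does not remove it either, because neither changes the expected value of the contrast. If one source comes out ahead, the documents as written would let the result be reported as an unbiased finding about cells, when part of it could be a response to having, or not having, a harvest.

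**Working it through.** **Inputs.** SD of VAS change 3.5, design difference 1.5 points, 121 per group for power and 90% retention at 1 year (9.2). Enrolment of 120 cell and 40 CSI subjects per arm over four sites (1.1, 6.2.2). Two-sided 0.05/6 = 0.0083 per pair (9.3.2), critical value z = 2.638. The size of any procedure effect is not in the documents; 0 to 1.5 points is an assumption.

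**The plan's own figures.** A two-sample equal-variance t-test with 121 per group gives 91.3% power for 1.5 points (stated: 91%) and 97.2% for 10 KOOS points with SD 20 (stated: 97%). Both reproduce.

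**What the direct contrast estimates.** Let C be a product's effect and P the effect of its procedure on reported pain, taken as additive. Then E[cell A − cell B] = (C_A − C_B) + (P_A − P_B). With equal cells, the expected difference is P_A − P_B, and none of it cancels.

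**Rejection rate when the cells are equal.** SE = 3.5 × √(2/120) = 0.452. With net procedure effect d, the rate is Φ(d/0.452 − 2.638) + Φ(−d/0.452 − 2.638).

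| Assumed d (VAS points) | n = 120 per group | n = 108 (90% retention) |
|---|---|---|
| 0 | 0.8% | 0.8% |
| 0.25 | 1.9% | 1.8% |
| 0.5 | 6.3% | 5.6% |
| 0.75 | 16.4% | 14.4% |
| 1.0 | 33.5% | 29.5% |
| 1.5 | 75.2% | 69.5% |

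These use the simple two-sample SE behind the sample size, not the mixed model's SE.

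**How this differs from cells versus pooled CSI.** One third of the pooled CSI group comes from each arm. If both harvests had the same effect P, and no harvest had none, the bias against pooled CSI would be P − 2P/3 = +P/3 for BMAC and SVF, and 0 − 2P/3 = −2P/3 for UCT. The effect cancels fully only against the CSI group of the same arm.

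**What the existing data can add.**
- Arm-referenced contrast, (cell A − CSI in arm A) − (cell B − CSI in arm B): SE = 3.5 × √(2/120 + 2/40) = 0.904, exactly twice 0.452. Power for 1.5 points at 0.0083 is 16%, against 75% for the direct test.
- CSI in one arm against CSI in another: SE = 3.5 × √(2/40) = 0.783, and 95% half-width 1.96 × 0.783 = 1.53 points.

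**Could the arm-referenced contrast act as a gate?** With equal cells, its estimate and the direct estimate have correlation 0.452/0.904 = 0.5, because they share the cell means. Among false-positive direct tests at d = 0.25, 0.5 and 1.0, it has the same sign in 92%, 87% and 73%. A same-direction condition would pass most of the errors it was meant to stop.

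**The case against.** **The trial is not open-label.** A reader might infer that three of the six tests are open-label. The documents do not support that. Subjects know the procedure, not the injection, and every arm has the same 3:1 ratio of cells to CSI. Section 8.2.15.4 has all Arm 3 subjects give blood so that the immunogenicity test does not unmask them. The usual bias from knowing that one received the active product is therefore balanced across arms. What remains is a differential response to the harvest itself, or to knowing which cell source was on offer. This stands and narrows the point.

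**Procedure plus product is a legitimate question.** An autologous product cannot be given without its harvest, and the study title compares preparations. Arms are randomized and baseline PROs are taken at screening, so this is not selection bias. That is a defensible estimand, but it is not what section 6.2 claims, which is efficacy of the cells.

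**The size is assumed.** The direction is also open: expectation could favour the harvest arms, and harvest pain could count against them. Section 2.3.1 describes discomfort around the procedure, whereas the sample size concerns change to 1 year. A net 1.0 point equals the whole decline that section 9.2 assumes for the control arm, and for BMAC-SVF it would have to be the difference between two harvests. All of this stands; the larger rates in the table are not predictions.

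**The separate SAP may handle it.** Section 9.3 calls itself a summary of an SAP whose fuller text is not in the document reviewed. A procedure term there would change the analysis point. It would not mask the procedure or alter the wording of 6.2.

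**Conclusion.** The point holds in a limited form. Procedure and cell source are fully aliased in the three cell-versus-cell tests, the procedure is known to the subject, and the endpoints are patient-reported. The lack of bias that section 6.2 asserts for autologous versus third-party cells is therefore not a property of the design. That sentence reaches BMAC-UCT and SVF-UCT; BMAC-SVF shares the confounding but is outside it.

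The size depends on an unknown. If the cells are equal and procedure effects are additive, a net VAS effect of 0.25, 0.5 or 1.0 point takes one test's rejection rate from 0.8% to 1.9%, 6.3% or 33.5% (SD 3.5, 120 per group). With no net procedure effect there is no bias.

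Two further inferences are not supported. First, the documents do not show that the cell-versus-cell results will be biased, or in which direction. Second, the 40 CSI subjects per arm cannot settle the matter: a half-width of 1.53 points is wider than the 1.5-point design difference, so those data could not exclude an effect of that size.

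**What to change.** 1. **Section 6.2.** Limit the word unbiased to cells versus CSI within the same arm. Describe the three cell-versus-cell tests as comparisons of harvest procedure plus product, with the procedure known to the subject and the injection (cells or CSI) masked.
2. **Section 9.3.2, unchanged.** Keep the six planned pairwise tests and the Bonferroni rule.
3. **Section 9.3.2, added.** Prespecify six supportive estimates with 95% intervals: (cell A − CSI in arm A) − (cell B − CSI in arm B) for each of the three cell pairs, and the three CSI-to-CSI differences between arms. State that they are not a condition for any claim, and that any claim of a superior source will be interpreted alongside them.

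**Cost.** Some wording and six contrasts from data already being collected; no change to design, sample size or the multiplicity plan. The analysis data must keep the arm in which each CSI subject was randomized. The downside is imprecision (VAS SE 0.90 and 0.78, against 0.45 for the direct test): the estimates inform but cannot exclude a procedure effect, and the claim about cell source becomes more modest.
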